10.3 Analysis Populations

The Per-protocol (PP) set will include all randomized patients who have received at least three months treatment with a study dialyzer and do not have any major protocol violations that might impact the primary analyses.

The intent-to-treat full analysis (FA) set will include all randomized patients.

The primary analyses will be performed on the FA set and supported by an analysis using the PP set. All other analyses will be performed on the FA set unless otherwise noted.

10.4 Demographics and Baseline Characteristics

Continuous demographic and baseline characteristics including age, height, screening laboratory tests and screening vital signs will be summarized descriptively by treatment group and overall using sample size (N), mean, SD, minimum and maximum. A t-test will be used to evaluate mean differences between treatment groups or a non-parametric procedure, as appropriate.

Categorical demographic and baseline characteristics including gender, race and medical history will be summarized descriptively by treatment group using frequencies and percentages. Treatment group comparability will be evaluated using Fisher's exact test. Medical history; medical condition or surgery items collected on the eCRF will be coded

to the appropriate System Organ Class (SOC) and Preferred Term (PT) using the Medical Dictionary for Regulatory Activities (MedDRA), Version 18 or higher.

10.5 Primary Endpoint(s)

The primary endpoints will be analyzed in a hierarchical manner, starting with the primary safety endpoint.

The primary analyses will be performed using a multiple imputation approach. Multiple imputations using SAS Proc MI will be used to impute missing data under the missing at random assumption and the data sets generated will be analyzed using SAS Proc MIANALYZE. It is expected that the missing values will be monotone (i.e., when a variable Y_j is missing for an individual i , then subsequent variables Y_k , $k > j$, are all missing for the individual i). Thus, the regression method for imputation will be used. Using the primary safety analysis as an example, if a subject is missing serum albumin values at weeks 20 and 24, a regression model is first fitted using the non-missing values prior to week 20 (baseline, weeks 4, 8, 12, and 16) in order to impute the missing value for week 20. This method is then repeated in order to impute the missing value for week 24 using the non-missing values of the prior weeks plus the newly imputed value for week 20.

Twenty complete data sets will be analyzed for the multiple imputation of the primary endpoint data. The impact of missing data on the primary safety and efficacy analyses will be further explored as sensitivity analyses using observed data as well as last observation carried forward.

10.5.1 Primary Safety Endpoint(s)

For the primary safety endpoint of pre-dialysis serum albumin after 24 weeks of treatment, let μ_T denote the Theranova dialyzer pre-dialysis serum albumin mean and let μ_R denote the Elisio-17H dialyzer pre-dialysis serum albumin mean. Then the null hypothesis to demonstrate non-inferiority using a 5% margin can be expressed as:

$H_0: \mu_T - \mu_R \leq -1.765$. The alternative hypothesis is expressed as $H_a: \mu_T - \mu_R > -1.765$.

An ANCOVA model with fixed effects of treatment and site and the continuous fixed covariate of baseline pre-dialysis serum albumin will be used to generate a two-sided 95% confidence interval (CI) for the difference in treatment means ($\mu_T - \mu_R$). If the lower bound is > -1.765 then non-inferiority will be demonstrated.

10.5.2 Primary Efficacy Endpoint(s)

For the primary efficacy endpoint of RR of λ FLC after 24 weeks of treatment, let μ_T denote the Theranova dialyzer RR of λ FLC mean at 24 weeks and let μ_R denote the Elisio-17H dialyzer RR of λ FLC mean at 24 weeks. Then the null hypothesis to demonstrate superiority can be expressed as:

$H_0: \mu_T - \mu_R = 0$. The alternative hypothesis is expressed as $H_a: \mu_T - \mu_R \neq 0$.

The primary safety analysis will be conducted first. If the primary safety analysis demonstrates non-inferiority, an ANCOVA model with fixed effects of treatment and site will be used to generate a two-sided 95% CI for the difference in treatment means ($\mu_T - \mu_R$). If the lower bound is > 0 then superiority will be demonstrated. The statistical testing of the primary efficacy endpoint of the reduction ratio (RR) of λ FLC after 24 weeks of treatment is contingent upon the outcome of the analysis of the primary safety endpoint and will only be conducted once non-inferiority could be established for the primary safety endpoint. This hierarchical testing approach guarantees that the overall type 1 error is controlled at a two-sided 0.05 significance level.

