A previously conducted Theranova 400 dialyzer prototype HDF study (Comparison of the Clinical Performance of Two Theranova 400 Dialyzer Prototypes in Hemodialysis Mode with the Performance of a High-Flux Dialyzer in Hemodialysis Mode and a High-Flux Dialyzer in High-volume Hemodiafiltration Mode – A Pilot Study, registered at clinicaltrials.gov, NCT02377622) was used to obtain λ FLC reduction ratio mean and standard deviation (SD) of 37.8 and 8.26. With a total sample size of 140 evaluable subjects as determined based on the primary safety endpoint (70 in the Theranova 400 dialyzer treatment group and 70 in the Elisio-17H dialyzer treatment group), a difference of 4.56 in the λ FLC reduction ratio in favor of the Theranova 400 dialyzer can be detected with 90% power at a two-sided 0.05 significance level using a two-sided two-sample t-test assuming equal variances. The sample size calculation for the primary efficacy endpoint was performed using PASS® 15.0.1 software, procedure Two-Sample T-Test Assuming Equal Variance.

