9.3 Clinical Laboratory Evaluations

- Date and time lab sample collected (listing only)
- Initial / re-test (listing only)
- Accession / sample number (listing only)

Table 7: List of Laboratory Tests

(Test on screening pre-dialysis):

- β-hCG (if applicable)
- Hepatitis A, B and C
- Human Immunodeficiency Virus

(Test on screening pre-dialysis, 1st treatment day pre-dialysis, week 4 pre-/post-dialysis and week 24 pre-/post-dialysis):

- λ FLC
- κ FLC

(Test on 1st treatment day pre-dialysis, week 4 pre-/post-dialysis and week 24 pre-/post-dialysis):

- β2-microglobulin
- CFD
- IL-6
- TNFα

(Test on 1st treatment day pre-dialysis, week 12 predialysis, week 24 pre-dialysis and end of study predialysis):

- Factor II
- Factor VII
- Protein C

(Test on 1st treatment day pre-dialysis, week 4 pre-dialysis, week 24 pre-dialysis and end of study pre-dialysis):

• Vitamin A

(Test on every visit pre-dialysis besides end of study pre-dialysis):

• hs-CRP

Serum Chemistry: (Test on every visit pre-dialysis):

• Albumin

(Test on every visit pre-/post-dialysis besides 1st treatment day and end of study):

• BUN

(Test on screening pre-dialysis, 1st treatment day pre-dialysis, week 12 pre-dialysis and end of study pre-dialysis):

• Phosphorus

Coagulation (test on screening pre-dialysis, week 12 pre-dialysis and end of study pre-dialysis):

- Prothrombin time
- INR
- Activated partial thromboplastin time

Comprehensive Metabolic Panel (test on screening pre-dialysis, 1st treatment day pre-dialysis, week 12 pre-dialysis and end of study pre-dialysis):

• Bicarbonate

Hematology (test on screening pre-dialysis, 1st treatment day pre-dialysis, week 12 pre-dialysis and end of study pre-dialysis):

- Calcium
- Chloride
- Creatinine
- Glucose
- Sodium
- Potassium

Liver Function (test on screening pre-dialysis, week 12 pre-dialysis and end of study pre-dialysis):

- Alkaline phosphatase
- ALT; SGPT
- AST; SGOT
- Direct bilirubin
- Gamma-glutamyl transferase
- Globulin
- Total bilirubin
- Total protein

- Hematocrit
- Hemoglobin
- Mean corpuscular hemoglobin
- Mean corpuscular hemoglobin concentration
- Mean corpuscular volume
- Platelet count
- Red blood cell count
- White blood cell count with differential

Lipids (test on screening pre-dialysis, 1st treatment day pre-dialysis, week 12 pre-dialysis and end of study pre-dialysis):

- Total cholesterol
- HDL cholesterol
- LDL cholesterol
- Triglycerides

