12.1 Primary Analysis

For the primary efficacy endpoint of RR of λ FLC after 24 weeks of treatment, let μ_T denote the Theranova 400 dialyzer RR of λ FLC mean at 24 weeks and let μ_R denote the Elisio-17H dialyzer RR of λ FLC mean at 24 weeks. Then the null hypothesis to demonstrate superiority can be expressed as:

Ho: μ_T - $\mu_R = 0$. The alternative hypothesis is expressed as Ha: μ_T - $\mu_R \neq 0$.

The primary safety analysis will be conducted first. If the primary safety analysis demonstrates non-inferiority, an ANCOVA model with fixed effects of treatment and site will be used to generate a two-sided 95% CI for the difference in treatment means (μ_T - μ_R). If the lower bound is > 0 then superiority will be demonstrated. The statistical testing of the primary efficacy endpoint of the reduction ratio (RR) of λ FLC after 24 weeks of

treatment is contingent upon the outcome of the analysis of the primary safety endpoint and will only be conducted once non-inferiority could be established for the primary safety endpoint. This hierarchical testing approach guarantees that the overall Type I error is controlled at a two-sided 0.05 significance level.

The primary efficacy analyses will be performed using a multiple imputation approach. Multiple imputations using SAS Proc MI will be used to impute missing data under the missing at random assumption and the data sets generated will be analyzed using SAS Proc MIANALYZE (for more detail on missing data imputation see Section 7.2.2).

Twenty (20) complete data sets will be analyzed for the multiple imputation of the primary endpoint data.

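### The primary efficacy model is called an ANCOVA but has no continuous covariate; pre-specifying two baseline values already collected may add precision at almost no cost

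*Protocol*

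**What the plan says.** Protocol 10.5.2 specifies for the λ FLC reduction ratio at Week 24 that "an ANCOVA model with fixed effects of treatment and site will be used to generate a two-sided 95% CI for the difference in treatment means". The synopsis gives the same model, and SAP 12.1 repeats it: "an ANCOVA model with fixed effects of treatment and site will be used". Neither document names a continuous covariate or gives a reason for leaving one out.

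The primary safety model differs. Protocol 10.5.1 uses "fixed effects of treatment and site and the continuous fixed covariate of baseline pre-dialysis serum albumin". The ANCOVA for change in pre-dialysis β2-microglobulin (protocol 10.6.2, SAP 12.3) also adjusts for baseline.

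Two relevant quantities are measured before the first study treatment. SAP 9.3 (Table 7) schedules λ FLC as "Test on screening pre-dialysis, 1st treatment day pre-dialysis, week 4 pre-/post-dialysis and week 24 pre-/post-dialysis" and BUN as "Test on every visit pre-/post-dialysis besides 1st treatment day and end of study". A pre-dialysis λ FLC is therefore available at screening and on Day 1, and a pre/post BUN pair at screening. The laboratory schedules (protocol Appendix 2, SAP Table 2) agree.

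For power, protocol 10.2 cites an earlier prototype study that "was used to obtain λ FLC reduction ratio mean and standard deviation (SD) of 37.8 and 8.26". It states that "a difference of 4.56 in the λ FLC reduction ratio in favor of the Theranova 400 dialyzer can be detected with 90% power" with 70 evaluable patients per group, "at a two-sided 0.05 significance level using a two-sided two-sample t-test assuming equal variances".

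**The concern.** An analysis of covariance without a covariate is either mislabelled or incomplete. If a value measured before treatment predicts the Week 24 RR, adjusting for it shrinks the residual variance, narrows the primary interval and protects against chance imbalance between arms. It does not affect type I error when fixed in advance.

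A link is plausible. The RR is a within-session removal fraction, session length varies with patient need (protocol 5.3), and treatment time and flow rates are meant to stay stable (protocol 3.4). Differences between patients in dialysis dose may therefore persist to Week 24.

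Imputation is also affected. The SAP 7.2.2 example uses albumin, which has baseline and five on-treatment visits before Week 24. The λ FLC RR has only Week 4 before Week 24. A patient who leaves before Week 4 has no earlier RR, and the SAP names no other predictor.

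**Working it through.** **Inputs** (protocol 10.2, SAP 5.3): 70 evaluable patients per arm, SD 8.26, difference 4.56, two-sided α 0.05. The correlation r is an assumption. It is the within-arm, site-adjusted (multiple) correlation of the covariates with the Week 24 RR. It is not a share of variance; that share is r².

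**1. The plan's own figure.**
- Standard error = 8.26 × √(2/70) = 1.396.
- Noncentrality = 4.56 / 1.396 = 3.27, on 138 degrees of freedom.
- Noncentral-t power = 0.9003, and the difference detectable with 90% power is 4.558. The plan's figure reproduces without a covariate.
- 95% CI half-width = 2.761.

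**2. With covariates.** Residual SD = 8.26 × √(1 − r²), with one degree of freedom removed. For example, at r = 0.3 the residual SD is 8.26 × √0.91 = 7.880, the standard error is 1.332, the noncentrality is 3.42 and power is 92.5%.

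| r (assumed) | r² | Residual SD | CI half-width | CI narrower by | Power at 4.56 | Detectable at 90% |
|---|---|---|---|---|---|---|
| 0 | 0% | 8.260 | 2.761 | – | 90.0% | 4.558 |
| 0.1 | 1% | 8.219 | 2.747 | 0.5% | 90.3% | 4.535 |
| 0.2 | 4% | 8.093 | 2.705 | 2.0% | 91.2% | 4.466 |
| 0.3 | 9% | 7.880 | 2.634 | 4.6% | 92.5% | 4.348 |
| 0.4 | 16% | 7.570 | 2.530 | 8.3% | 94.3% | 4.177 |
| 0.5 | 25% | 7.153 | 2.391 | 13.4% | 96.3% | 3.947 |

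**3. Site terms.** With 30 site terms the degrees of freedom before any covariate fall to 109. Power becomes 89.9% at r = 0, 92.4% at r = 0.3 and 96.2% at r = 0.5, a change of about 0.1 point or less. A second covariate costs one more degree of freedom, which is smaller still.

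**4. Sample size.** For albumin, with margin 1.765 (5% of 35.3), SD 3.7, 70 per arm and one-sided 0.025, noncentral-t power is 0.8002. Allowing for dropout, 70 / 0.85 = 82.4, so 83 per arm and 166 in total. Albumin sets this number, and adjusting the efficacy model does not change it.

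**5. Which covariates the data support.**
- *Baseline λ FLC RR:* not available. Protocol 3.2.2 lists a first-day RR, but the schedules have no Day 1 post-dialysis λ FLC sample. Such an RR would in any case come from the first session on the randomized dialyzer.
- *Week 4 RR:* measured on study treatment, so not a valid covariate for the treatment comparison. It can remain an imputation predictor.
- *Day 1 pre-dialysis λ FLC:* available, and drawn before first exposure to the study dialyzer.
- *Screening urea reduction ratio:* (1 − post/pre BUN) × 100, which needs only the screening BUN pair.
- *Screening Kt/V:* not clearly available. The formula in protocol Appendix 3 needs treatment time and weight loss. Appendix 1 shows a single screening body-weight entry, and its footnote ties ultrafiltration to the 4-week treatment periods although the screening box is ticked.

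**The case against.** The strongest reply is that nothing in the plan fails. The comparison is randomized, site is already in the model to match the stratification, and the stated power is reached unadjusted. All of that stands.

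The contrast with albumin also has an explanation. Albumin has a true baseline of the same variable, whereas the RR has none, and the RR models for the secondary endpoints carry no baseline either. This accounts for the pattern, but not for the ANCOVA label or for passing over other baseline predictors.

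The candidates may also be weak. Day 1 λ FLC is a concentration, while the RR already divides by its own pre-dialysis level. Screening urea removal is measured on the pre-study dialyzer, and protocol 1.1 itself notes that diffusive clearance drops quickly as molecules get larger. Site effects may already absorb part of the variation in dose. These points stand and are why small values of r belong in the range.

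A reader might infer that precision is in fact being given away, or that the efficacy test is underpowered or invalid. The documents do not support either inference. They report no correlation between any baseline variable and the Week 24 RR, and at r of 0.2 or less the gain is about one power point.

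**Conclusion.** The efficacy model is an ANCOVA in name only, and precision may be lost. The omission does not bias the estimate, invalidate the interval, inflate type I error or undercut the stated 90% power.

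The possible gain is negligible at r = 0.1, about one power point at r = 0.2, and modest at r = 0.3 to 0.5 (power 92.5% to 96.3%, interval 4.6% to 13.4% narrower). These figures rest on the assumed r, the plan's SD of 8.26 and 70 evaluable patients per arm. Because the covariates are already measured and cost about two degrees of freedom, this is a nearly free improvement, not the correction of an error.

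**What to change.** Before database lock, amend SAP 12.1 so that the Week 24 λ FLC RR model contains treatment, site, log Day 1 pre-dialysis λ FLC and the screening urea reduction ratio, the last two as continuous fixed covariates. In SAP 7.2.2, place both in the imputation model for λ FLC RR ahead of the Week 4 RR. State that the Week 4 RR is not a covariate in the analysis model. Record the change in SAP section 10, since protocol 10.5.2 names the present model.

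If the sponsor prefers no covariate, the minimum is to call the model a two-way ANOVA and say why.

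The cost is a few sentences in the SAP and two degrees of freedom, with no new samples and no change to the 166 randomized. The timing matters because the trial is open-label: covariates chosen after the data are seen would invite a charge of selection.

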10.6 Secondary Endpoint(s)

10.6.1 Secondary Safety Endpoint(s)

Pre-dialysis serum albumin:

A Mixed-effect Model Repeated Measurement (MMRM) model will be used to evaluate differences between treatment groups in the change from baseline in pre-dialysis serum albumin after each four weeks of treatment. The model will include the fixed effect of treatment, visit; the continuous, fixed covariate of baseline measurement; and the random effect of patient.

Pre-dialysis serum albumin will be further categorized at baseline and final measurement into 4 categories: <3.5 , $\geq 3.5-3.9$, $\geq 4.0-4.4$, ≥ 4.5 . Shift tables will be generated to cross tabulate the number of patients within each category by treatment.

Pre-dialysis Factor VII, Protein C, Vitamin A, and Factor II:

An MMRM model will be used to evaluate the differences between treatment groups in the change from baseline in pre-dialysis Factor VII, Protein C, Vitamin A, and Factor II after 4 weeks and after 24 weeks of treatment. The model will include the fixed effect of treatment, visit; the continuous, fixed covariate of baseline measurement; and the random effect of patient.

nPNA (nPCR):

An MMRM model will be used to evaluate differences between treatment groups in nPNA(nPCR) collected after each 4 weeks of treatment. The model will include the fixed effect of treatment, visit, and the random effect of patient.

AEs, SAEs, and Product Complaints:

The summary of AEs will include AEs that occur on the day of or after the first study treatment. AEs will be mapped to a Primary SOC and PT according to MedDRA and summarized descriptively by SOC, PT and treatment group. Treatment group comparability in the incidence rates of adverse events will be evaluated using Fisher's exact test.

An overview (overall) summary table of all AEs will be generated that includes the total number of AEs, number and percentage of patients with at least one AE, number and percentage of patients with at least one SAE, number and percentage of patients with at least one severe AE, number and percentage of patients with at least one AE probably associated with study treatment, number and percentage of patients with an AE leading to study discontinuation and number and percentage of patients with an AE leading to death. This summary table will be presented by treatment group and combining both groups (Total).

Furthermore, separate AE summary tables will be provided by SOC and PT for SAEs and AEs leading to study withdrawal. Separate AE summary tables will be provided to show a breakdown of AEs by SOC, PT and

- a. severity (mild, moderate or severe),
- b. relationship to study treatment (probably related, possibly related, unable to determine, unlikely related or not related).

Study dialyzer related product complaints will be summarized descriptively by study dialyzer.

Chemistry and hematology:

Mean differences between treatment groups in the change from baseline to final measure in chemistry and hematology laboratory tests will be analyzed using an ANCOVA with a fixed effect of treatment and a fixed continuous covariate of baseline laboratory value.

10.6.2 Secondary Efficacy Endpoint(s)

In order to account for multiplicity, secondary efficacy analyses will be held to a hierarchical assessment and performed in the order outlined below. If the first analysis results in a p-value <0.05 , then formal testing will continue to the second analysis. If the second analysis also results in a p-value <0.05 , then formal testing will continue to the third analysis, and so on. This method of hierarchical assessment will continue until an analysis results in a p-value > 0.05 , i.e., is considered statistically insignificant. This hierarchical approach guarantees that the overall alpha will not exceed 0.05.

1. MMRM of reduction ratio of λ FLC
2. MMRM of reduction ratio of CFD
3. MMRM of reduction ratio of κ FLC
4. MMRM of reduction ratio of IL-6
5. MMRM of reduction ratio of TNF α
6. MMRM of reduction ratio of β_2 -microglobulin
7. Change in pre-dialysis β_2 -microglobulin from baseline to 24 weeks
8. MMRM of Kt/V_{urea}

An MMRM model will be used to evaluate differences between treatment groups in the reduction ratios of λ FLC, CFD, κ FLC, IL-6, TNF α , β_2 -microglobulin after 4 weeks and after 24 weeks of treatment. The model will include the fixed effect of treatment, visit, and the random effect of patient.

An ANCOVA with a fixed effect of treatment and a fixed continuous effect of baseline pre-dialysis β_2 -microglobulin will be used to evaluate differences between treatment groups for the change from baseline in pre-dialysis β_2 -microglobulin after 24 weeks of treatment.

An MMRM model will be used to evaluate differences between treatment groups in Kt/V_{urea} collected after each 4 weeks of treatment. The model will include the fixed effect of treatment, visit, and the random effect of patient.

10.7 Exploratory Endpoints

An MMRM model will be used to evaluate differences between treatment groups in the change from baseline in pre-dialysis serum levels of hs-CRP after each 4 weeks of treatment. The model will include the fixed effect of treatment, visit, as well as the continuous, fixed covariate of baseline measurement and the random effect of patient.

An MMRM model will be used to evaluate differences between treatment groups in the change from first day of treatment in KDQOL-36 and EQ-5D-5L after 12 weeks and after 24 weeks of treatment. The model will include the fixed effect of treatment, visit, as well as the continuous, fixed covariate of screening measurement and the random effect of patient.

Appropriate models will be used to evaluate differences between treatment groups in the utilization for medications (i.e., ESA, anti-hypertensives, iron).

